Before any study-related procedures are performed, voluntary, written, study-specific informed consent will be obtained from the subjects. **Subjects will be screened at Visit 1.** All subjects will have blood sampling for hematology and biochemistry. After checking the eligibility of the subject at Visit 2, the randomization number and adjoining study intervention allocation will be assigned. **Subjects in lot-to-lot consistency and immunogenicity group will have blood drawn for immunogenicity before vaccination.** Unblinded site staff member(s) will dispense/administer 0.5 mL UB-612/placebo into the deltoid muscle of the preferably nondominant arm. Blinded site staff must observe the subject for at least 30 minutes after study vaccine administration for changes in vital signs or any acute anaphylactic reactions. The investigator will provide instructions for reactogenicity e-diary completion and ask the subject to complete the reactogenicity e-diary from

Day 1 to Day 7, skin allergic reaction e-diary from Day 1 to Day 14, with Day 1 being the day of vaccination. Participants will be instructed to contact the site staff or investigator immediately if he or she experiences any of the Grade 3/4 AEs from Day 1 to Day 7 to determine if an unscheduled reactogenicity visit is required. Apart from reactogenicity, allergic skin rash should be monitored for 14 days post vaccination. **Once subject encountered the Grade 3/4 allergic skin rash, site staff should call for detail to evaluate the necessity of unscheduled visit. Investigators could ask for HLA typing survey if he/she concerned about the possibility of hypersensitivity. Of course, IDMC could also request HLA typing once they reviewed the safety data.**

At Visit 3 (Day 29), the 2nd study vaccine administration will be done and subjects will be closely monitored for 30 minutes after vaccination for changes in vital signs or acute anaphylactic reaction. The 7/14-day post-vaccination e-diary will be given to subjects with a suitable instruction. For females of child-bearing potential, a urine pregnancy test will be performed before vaccination and found negative. At Visit 4 (Day 57, 1-month follow-up visit after 2nd vaccination), collect sample for safety and immunogenicity, review the participants' reactogenicity e-diary data and record any unsolicited AE.

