8.1.3 Day 8, 15, and 22 –Safety calls

Safety calls on Day 8, Day 15 and Day 22 to monitor subjects' unsolicited AEs and symptoms of COVID-19. Calls on Day 8 and Day 15 should be inquire the phenomenon of allergic skin reaction, especially itching and redness, or other unsolicited allergy reaction. No matter injection site or extending to other body site, site staff should arrange unscheduled visit to verify the allergic reaction and check HLA typing if indicated.

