8.1.4 Visit 3 (Day 29 ± 3 day) –2nd Vaccination

- (1) Check contraindication for second vaccination and the possibility of delay vaccination
- (2) Conduct physical examination.
- (3) Measure vital signs.
- (4) Perform a urine pregnancy test.
- (5) If subject encountered \geq Grade 3 hypertension, subject should be checked the existence or deterioration of proteinuria or other renal damage sign.
- (6) Collect blood sample before vaccination for following tests only for subjects in lot-to-lot consistency/immunogenicity only:
 - Anti-RBD-S1 antibody
- (7) Perform 2nd vaccination by unblinded administrator.
- (8) Observe closely during vaccination and at least 30 minutes after vaccine administration for the change of vital sign or acute anaphylactic event at site by blinded site staff.
- (9) Instruct the subject to monitor body temperature and complete self-evaluation e-diary correctly.

Subject will be instructed to record any solicited adverse events occurring during a 7-day post-vaccination period on the e-diary system. Meanwhile, skin allergic reaction should be monitored for 14 days via e-diary. If the subject perceives any signs or

symptoms are progressing or serious, contact the investigator or their delegates immediately. Additional return visits can be scheduled by the investigators when necessary.

- (10) Review concomitant medications.
- (11) Record and report adverse event, serious adverse event, or any symptoms of COVID-19 if any has occurred since the previous visit.

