8.1.5 Day 36 and 43 –Safety calls

Safety calls on Day 36 and 43 to monitor subjects' unsolicited AEs and symptoms of COVID-19.

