8.1.9 Visit 6 (Day 197~242) –3rd Vaccination

The following procedures will only be performed on subjects who agreed to have 3rd vaccination. The Visit 5 and Visit 6 could be the same day.

- (1) Collect informed consent form for vaccine group who agreed to have 3rd vaccination.**
- (2) Check contraindication for the third vaccination and the possibility of delay vaccination**
- (3) Conduct physical examination.**
- (4) Measure vital signs.**
- (5) Perform a urine pregnancy test.**
- (6) If subject encountered \geq Grade 3 hypertension, subject should be checked the existence or deterioration of proteinuria or other renal damage sign.**
- (7) Collect blood sample for following tests:**
 - **Immune response assessments**
 - **Blood routine tests**
 - **Biochemistry test**
 - **Immunology test**
 - **T cell function (optional)**
- (8) Perform 3rd vaccination**
- (9) Observe closely during vaccination and at least 30 minutes after vaccine administration for the change of vital sign or acute anaphylactic event at site by site staff.**
- (10) Instruct the subject to monitor body temperature and complete self-evaluation e-diary correctly.**

(11) Review concomitant medications.

(12) Conduct COVID-19 surveillance

(13) Record and report adverse event, serious adverse event, or any symptoms of COVID-19 if any has occurred since the previous visit.

8.1.10 Safety call on 7 days after Visit 6 (Only for subjects who have 3rd vaccination)

Safety calls on 7 days after Visit 6 to monitor subjects' unsolicited AEs and symptoms of COVID-19. Call should be inquired the phenomenon of allergic skin reaction, especially itching and redness, or other unsolicited allergy reaction. No matter injection site or extending to other body site, site staff should arrange unscheduled visit to verify the allergic reaction and check HLA typing if indicated.

8.1.11 Follow up on 14 days after Visit 6 (\pm 3 day) (Only for subjects who have 3rd vaccination)

(1) Conduct physical examination.

(2) Measure vital signs.

(3) If subject encountered \geq Grade 3 hypertension, subject should be checked the existence or deterioration of proteinuria or other renal damage sign.

(4) Collect blood sample for following tests:

➤ **Immune response assessments**

➤ **Blood routine tests**

➤ **Biochemistry test**

➤ **Immunology test**

➤ **T cell function (optional)**

(5) Review concomitant medications.

(6) Conduct COVID-19 surveillance

(7) Record and report adverse or serious adverse event.

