9.5.5 Self-Evaluation/Reporting (Solicited/Unsolicited Symptoms)

9.5.5.1 Solicited Symptoms

Information of solicited symptoms and body temperature will be collected by the subjects in the provided e-diary cards during a 7-day follow-up period after each vaccination (i.e. day of vaccination and 6 subsequent days), and reported by the investigator team. Meanwhile, skin allergic reaction should be monitored for 14 days via e diary. The subject should complete the assessments in the e-diary every evening.

Local reaction, skin allergic reaction, and systemic event are the one whose nature or intensity is consistent with the expected AEs described and listed below.

Table 9-1 Grading for local reaction

Local Reaction	Mild (Grade 1)	Moderate (Grade 2)	Severe (Grade 3)	Potentially Life Threatening (Grade 4)
Pain at injection site	Does not interfere with activity	Interferes with activity	Prevents daily activity	Emergency room visit or hospitalization for severe pain
Itching at injection site	Does not interfere with activity	Interferes with activity	Prevents daily activity	Emergency room visit or hospitalization for severe symptoms
Redness	>2.0 to 5.0 cm (5 to 10 measuring device units)	>5.0 to 10.0 cm (11 to 20 measuring device units)	>10 cm (≥21 measuring device units)	Necrosis or exfoliative dermatitis
Swelling	>2.0 to 5.0 cm (5 to 10 measuring device units)	>5.0 to 10.0 cm (11 to 20 measuring device units)	>10 cm (≥21 measuring device units)	Necrosis or exfoliative dermatitis

Table 9-2 Grading for allergic skin reaction

Local Reaction	Mild (Grade 1)	Moderate (Grade 2)	Severe (Grade 3)	Potentially Life Threatening (Grade 4)
Skin allergic reaction	Localized urticaria (wheals) with no medical intervention indicated	Localized urticaria with intervention indicated OR Mild angioedema with no medical intervention indicated	Generalized urticarial OR Angioedema with intervention indicated	Anaphylaxis

Table 9-3 Grading for systemic events

Systemic Event	Mild (Grade 1)	Moderate (Grade 2)	Severe (Grade 3)	Potentially Life Threatening (Grade 4)
Subjective fever	Does not interfere with activity	Some interference with activity	Prevents daily routine activity	Emergency room visit or hospitalization for severe symptoms
Chills	Does not interfere with activity	Some interference with activity	Prevents daily routine activity	Emergency room visit or hospitalization for severe chills

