9.5.8 Communication and Use of Technology

This study may employ various methods, such as e-dairy, telephone, or other communication pathway, to contact with participants for record and maintain the study information. The communication items include but not limited to:

- Record 7-day solicited symptoms and 14-day skin allergic reaction after vaccination in reactogenicity e-diary
- Record unsolicited AEs or/and symptoms of COVID-19 on Day 8, Day 15, Day 22, Day 36, Day 43, Day 64, Day 71, Day 78, Day 85, **the day on 7 days after Visit 6 (only for subjects receiving 3rd dose)**, Day 253, and Day 309 using telephone communication
- Record regular surveillance for COVID-19 illness in e-dairy. A prompt on their smartphone device to regularly surveillance for signs and symptoms of COVID-19 every week after Day 57. If any potential symptoms for COVID-19 illness is reported, a telephone call will be made between site staffs and subjects.
- Unscheduled visit set-up or visit reminders

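### V-205 section 8.1.5 leaves the allergy question out of the Day 36 and Day 43 calls after dose 2, although sections 8.1.3 and 8.1.10 require it after doses 1 and 3

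*Supplement*

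**What the plan says.** All references are to the V-205 (phase II) protocol.

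- **After dose 1 (8.1.3).** The Day 8 and Day 15 calls must ask about allergic skin reaction, with itching and redness named, and about other unsolicited allergy. Whatever the body site, "site staff should arrange unscheduled visit to verify the allergic reaction and check HLA typing if indicated".
- **After dose 2 (8.1.5).** The whole instruction is: "Safety calls on Day 36 and 43 to monitor subjects' unsolicited AEs and symptoms of COVID-19".
- **After dose 3 (8.1.10).** For the call 7 days after Visit 6: "Call should be inquired the phenomenon of allergic skin reaction, especially itching and redness, or other unsolicited allergy reaction". The sentence on the verification visit and HLA typing is repeated there.
- **List of contacts (9.5.8).** The telephone contacts are given one common content and no allergy item: "Record unsolicited AEs or/and symptoms of COVID-19 on Day 8, Day 15, Day 22, Day 36, Day 43".

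Other sections cover dose 2 in part. Solicited symptoms are "collected by the subjects in the provided e-diary cards during a 7-day follow-up period after each vaccination" (9.5.5.1). After dose 2, "skin allergic reaction should be monitored for 14 days via e-diary", and "Additional return visits can be scheduled by the investigators when necessary" (both 8.1.4, item 9). Section 7.1 asks for contact about an allergic skin reaction whatever its severity, and adds: "Investigators could ask for HLA typing survey if he/she concerned about the possibility of hypersensitivity".

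**The concern.** The protocol treats allergy as a matter for active enquiry. It names the signs, puts the question in the staff's mouths, and does so at set times after doses 1 and 3. The calls on Days 36 and 43 sit at the same distance from dose 2 as Days 8 and 15 do from dose 1, yet the question has gone and no reason is given.

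What is at stake is modest: how uniformly low-grade allergic signs are picked up from one dose to the next. The scheduled examination after dose 2 is not until Visit 4 (Day 57), nominally 28 days later. A transient reaction that nobody asks about on Day 36 or Day 43 may have cleared by then.

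**Working it through.** There is no planned figure to reproduce. The check is day arithmetic and a comparison of sections.

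**1. Are the calls comparable?** Dose 1 is on Day 1 (8.1.2) and dose 2 on Day 29 ± 3 days (8.1.4).
- Dose 1 calls: 8 − 1 = 7 days and 15 − 1 = 14 days.
- Dose 2 calls: 36 − 29 = 7 days and 43 − 29 = 14 days.

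The nominal times match. If the calls stay on fixed study days while dose 2 moves between Day 26 and Day 32, they fall 4 to 10 and 11 to 17 days after dose 2.

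**2. What does each call ask?**

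| Call | Unsolicited AEs and COVID-19 symptoms | Allergy question | Directed visit, HLA typing if indicated |
|---|---|---|---|
| Days 8 and 15 (8.1.3) | yes | yes | yes |
| Days 36 and 43 (8.1.5) | yes | no | no |
| 7 days after dose 3 (8.1.10) | yes | yes | yes |

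Sections 7.1 and 9.5.8 also describe the calls, and neither supplies the missing items.

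**3. What does the e-diary cover after dose 2?** The day of vaccination counts as the first day (9.5.5.1).
- Local and systemic reactions, 7 days: Days 29 to 35.
- Skin allergic reaction, 14 days: Days 29 to 42.
- Days on which only the skin-allergy item runs: Days 36 to 42, which is 7 days.

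Injection-site itching and redness are graded in Table 9-1, with the local reactions solicited for 7 days. The skin-allergy item is graded in Table 9-2, whose lowest grade is localized urticaria. On the protocol text, then, the two signs named in 8.1.3 are not expressly solicited by anyone on Days 36 to 42. The diary form itself is not in the documents, so what the 14-day item actually asks is unknown.

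**4. What is left uncovered?**
- Urticaria and worse after dose 2: solicited by the diary, with contact required at any severity. Covered.
- Injection-site itching or redness on Days 36 to 42: reportable as an unsolicited AE, but with no staff prompt.
- Allergy outside the skin: reportable as an unsolicited AE on the same calls, but with no staff prompt.

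**5. Scope.** Planned enrolment is about 3850 + 385 = 4235 subjects (10.2). The change touches two existing calls for each, made while treatment is still blinded.

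**The case against.** The case against is that this is editorial. Skin allergy after dose 2 is solicited every evening for 14 days, contact is required regardless of severity, unsolicited AEs are collected throughout, and the Day 43 call looks back over exactly the week in question. HLA typing is conditional even in 8.1.3 and can be requested after any dose. Dose 3 does not fully mirror dose 1 either: the 14-day follow-up in 8.1.11 is an in-person visit with no allergy question.

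Most of this stands, and it rules out some stronger readings:

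- *A reader might infer that allergy goes unmonitored after dose 2, or rests on spontaneous report.* The documents do not support that. The 14-day diary is solicited collection, and the contact rule in 7.1 applies after dose 2 as well.
- *A reader might infer that the directed visit should be copied to dose 2 for every low-grade reaction.* That is debatable. For a Grade 3 or 4 allergic rash, 7.1 has staff telephone first to judge whether a visit is needed, and 8.3 does the same for a Grade 3 local reaction. Copying 8.1.3 word for word would send a mild itch to clinic by rule while a severe reaction gets a call first. Section 8.3 also classes every AE recognised at an unscheduled visit as an MAAE, apart from confirmed COVID-19, and MAAEs are a primary safety endpoint (6.2).

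The objection does not remove the difference in the text. A diary whose skin-allergy grading begins at urticaria, plus a general AE enquiry, is not the same as a named question. The protocol itself judged that question worth asking after the other two doses.

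**Conclusion.** The omission is real and minor. After dose 2 the calls at 7 and 14 days lack an active staff question on allergy that the protocol requires at 7 and 14 days after dose 1 and at 7 days after dose 3. The practical gap is narrow: injection-site itching or redness during the 7 days after the local-reaction diary closes, and allergy outside the skin.

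Its effect cannot be put in numbers, because the documents give no rate of allergic reaction and no estimate of how many events the prompt would add. A reader might infer that the by-dose tables or the vaccine-placebo comparison are biased. Nothing in the documents shows this, and the calls have the same content in both arms and are made blind. Nor can it be inferred that subjects would go unchecked into dose 3: Visits 4 and 5 and the calls on Days 64 to 85 come first, and contraindications and eligibility are rechecked at Visit 6 (8.1.9, 9.3).

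The conclusion rests on sites following section 8.1 as written, and on Tables 9-1 and 9-2 reflecting what the diary solicits. If the 14-day diary item also asks about itching and redness, the gap shrinks further, leaving chiefly the prompt for non-skin allergy.

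**What to change.** Add the 8.1.3 allergy question (skin reaction, with itching and redness named, or other allergy) to the Day 36 and Day 43 calls in 8.1.5. Follow it with a sentence providing for an unscheduled verification visit and HLA typing where the investigator judges them indicated, rather than for every low-grade report.

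The cost is one or two sentences of protocol text, a few minutes on calls already scheduled, and some extra visits. AEs recognised at those visits will count as MAAEs under 8.3 and may slightly raise MAAE counts in that primary safety endpoint. Sample size, power and alpha are unaffected.

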8.1.6 Visit 4 (Day 57 ± 3 day) –Follow-up

- (1) Conduct physical examination.
- (2) Measure vital signs.
- (3) If subject encountered \geq Grade 3 hypertension, subject should be checked the existence or deterioration of proteinuria or other renal damage sign.
- (4) Collect blood sample for following tests for subjects in lot-to-lot consistency /immunogenicity group:
 - Immune response assessments
 - T cell function (optional)
- (5) Collect blood sample for following tests for all subjects:
 - Blood routine tests
 - Biochemistry test
 - Immunology test
 - **Spared sample (tests for detecting serum antibody against SARS-CoV-2 or further researches)**
- (6) Review concomitant medications.
- (7) Record and report adverse event, serious adverse event, or any symptoms of COVID-19 if any has occurred since the previous visit.

After Day 57, each week (i.e., every 7 days) the subject will receive a prompt on their smartphone device to regularly surveillance for signs and symptoms of COVID-19.

8.1.7 Day 64, Day 71, Day 78, and Day 85 –Safety calls

Safety calls on Day 64, Day 71, Day 78, and Day 85 to monitor subjects' unsolicited AEs and symptoms of COVID-19.

8.1.8 Visit 5 (Day 197 ± 15 days) –Unblinding / Early Termination

- (1) Conduct physical examination.
- (2) Measure vital signs.

- (3) If subject encountered \geq Grade 3 hypertension, subject should be checked the existence or deterioration of proteinuria or other renal damage sign.

(4) Unblinding

(5) Withdraw subjects who received placebo

- (6) Collect blood sample for following tests only for subjects in lot-to-lot consistency /immunogenicity group:
- Immune response assessments
- (7) Review concomitant medications.
- (8) Record and report adverse event, serious adverse event, or any symptoms of COVID-19 if any has occurred since the previous visit.

The subject will receive a prompt on their smartphone device to regularly surveillance for signs and symptoms of COVID-19 each week.

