6.2 Primary Endpoint(s)

Immunogenicity Endpoint(s)

- Geometric mean titer (GMT) of SARS-CoV-2 neutralizing antibody on Day 57
- Seroconversion rate (SCR) of SARS-CoV-2 neutralizing antibody on Day 57

Safety Endpoint(s)

- Local reactions for up to 7 days following each dose
- Systemic events for up to 7 days following each dose
- Unsolicited AEs from Day 1 to Day 57
- MAAEs and SAEs from Day 1 to Day 365
- AESIs and ADEs from Day 1 to Day 365

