All subjects will come back on Day 197, Visit 5, for immunogenicity persistence check in immunogenicity group and safety check for safety group. **Once subject completes Visit 5, he or she will be unblinded. Subjects received placebo will withdraw from the study and subjects who received UB-612 vaccine will be invited to join the extension study to determine the durability of the immune response and long-term safety after unblinding. Meanwhile, subjects in vaccine group will be encouraged to have a third dose of UB-612. All subjects who received UB-612 vaccine will be followed up for 12 months.**

All subjects will receive safety calls on Day 8, Day 15, Day 22, Day 36, Day 43, Day 64, Day 71, Day 78, Day 85, Day 253, and Day 309 that will serve both to monitor for unsolicited AEs or/and to monitor for symptoms of COVID-19. After Day 57, each week (i.e., every 7 days) the subject will receive a prompt on their smartphone device to regularly surveillance for signs and symptoms of COVID-19 and SAE. **Subjects who received 3rd dose of UB-612 will receive an extra safety call on 7 days post 3rd vaccination.**

If a Grade 3 local reaction, systemic event, or fever are reported in the reactogenicity e-diary, a telephone contact should occur to ascertain further details and determine whether a site visit is clinically indicated. If suspected Grade 4 local reaction systemic event and /or fever is reported in the reactogenicity e-diary, a site visit should occur to confirm whether the event meets the criteria for Grade 4. All subjects were encouraged to contact site staff once they encountered Grade 3/4 AE. Allergic skin reaction should be monitored for 14 days post vaccination and should be contacted regardless of severity.

If a subject experiences a febrile illness associated with respiratory symptoms, he or she is instructed to contact the site immediately. Subjects may utilize a COVID-19 illness e-diary to prompt him/her to report any symptoms.

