There are two interim reports for EUA application. The first is for safety follow up in core group, and the second is for lot-to-lot consistency. Also, an additional interim report of immunogenicity and safety in adolescents, will be submitted for indication extension.

The surveillance for COVID-19 will be conducted as part of the study. The serological evidences in case of confirmed and/or severe COVID-19 will be described for the change of antibody level in vaccinated subjects. All subjects would be included in the exploratory objectives of protective efficacy against COVID-19 if case detected.

Unblinding will be carried out when the subject in core group or supplementary group has completed Visit 5. Subjects who receive the placebo vaccine will allow to withdraw from the study.

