7.4.7 Blinding

This is an observer-blind study, as the physical appearance of the investigational vaccine candidates and the placebo may differ. Only the dispenser(s)/administrator(s) will be unblinded. These study staffs are responsible for receiving, dispensing, preparing and administering the study intervention. The investigational products should be administered in a manner that prevents the subjects to identifying their treatment based on vaccine physical appearance. The dispenser(s)/administrator(s) should not participate in any of the study clinical evaluations or assay, and keep minimum contacts with other study personnel.

Neither the subjects nor the investigators, sponsor staffs, clinical monitors, study coordinators other than dispenser(s)/administrator(s), or other site staff who involve in clinical evaluation of the subjects will be aware of the treatment received either at the time of randomization or later, throughout the conduct of the trial. **These study personnel will be blinded until Visit 5. Unblinding will be carried out via disclosed Randomization Envelop during Visit 5.**

The treatment codes will be not prematurely broken unless an emergency situation, when the appropriate management of the subject necessitated knowledge of the treatment allocation, occurred. In the event of a medical emergency, if possible, the clinical monitor should be contacted before the treatment code blind is broken to discuss the need for unblinding. For unblinding a

subject, the treatment code blind can be obtained by the investigator, by opening the emergency envelope.

The sponsor must be notified immediately if the treatment code blind is broken. The date, time, and reason that the blind is broken must be recorded in the source document and the same information (except the time) must be recorded on the eCRF.

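### V-205 contradicts itself on whether the code is opened, and placebo subjects withdrawn, before or after the Day 197 blood draw and adverse-event recording

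*Supplement*

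**What the plan says.** All references are to the Phase II protocol, V-205.

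Section 8.1.8 gives eight numbered steps for Visit 5 (Day 197). Steps 1 to 3 are the physical examination, vital signs and a conditional renal check. Step 4 is unblinding and step 5 is "Withdraw subjects who received placebo". Step 6 is the immunogenicity sample ("Collect blood sample for following tests only for subjects in lot-to-lot consistency /immunogenicity group"), step 7 is concomitant medication, and step 8 is "Record and report adverse event, serious adverse event, or any symptoms of COVID-19 if any has occurred since the previous visit".

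On the timing of unblinding:

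- Section 7.4.7 (Blinding): "Unblinding will be carried out via disclosed Randomization Envelop during Visit 5".
- Section 7.1, with the same sentence in the synopsis: "Once subject completes Visit 5, he or she will be unblinded".
- Section 7.3: "Unblinding will be carried out when the subject in core group or supplementary group has completed Visit 5".

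The synopsis and 7.1 also say, more loosely, that subjects are unblinded at Visit 5.

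The primary safety endpoints in section 6.2 include "MAAEs and SAEs from Day 1 to Day 365", with AESIs and ADEs over the same period. Reactogenicity covers 7 days after each dose, and the remaining item is "Unsolicited AEs from Day 1 to Day 57". Section 9.5.6.7 has the investigator judge causality for every AE and SAE other than solicited reactions, and section 10.5.1 compares the arms by Fisher's exact test. GMT and fold increase at Day 197 are secondary endpoints (6.4), compared between vaccine and placebo (10.6.2).

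**The concern.** Visit 5 is the last scheduled visit for placebo subjects and the end of the placebo-controlled period. The vaccine-versus-placebo comparison of MAAEs, SAEs, AESIs and ADEs rests on what has been recorded up to then.

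If the envelope is opened before step 8, subject and investigator both know the arm when they report and attribute events not previously captured. That can shift reporting and causality differently in the two arms, which is what the observer-blind design is meant to prevent. If placebo subjects are withdrawn before steps 6 to 8, their final event recording and their Day 197 sample depend on a person who has just left the study staying for the rest of the visit.

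**Working it through.** **The passages side by side**

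| Section | When the code is opened |
|---|---|
| 8.1.8 | Step 4 of 8, before sampling and event recording |
| 7.4.7 | During Visit 5 |
| Synopsis, 7.1 | Once the subject completes Visit 5 (also, loosely, at Visit 5) |
| 7.3 | When the subject has completed Visit 5 |

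The 8.1.8 order cannot be squared with the synopsis, 7.1 and 7.3: a visit is not complete with three listed steps outstanding. Section 7.4.7 does not settle the matter, because it allows the envelope to be opened part-way through the visit.

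**Which endpoints are exposed**

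- Reactogenicity (7 days after each of the two blinded doses) and unsolicited AEs (to Day 57) close before Visit 5. Not exposed.
- MAAE, SAE, AESI and ADE run to Day 365. Exposed only for events first recorded at Visit 5.
- Day 57 GMT and seroconversion, the primary immunogenicity endpoints. Not exposed.
- Day 197 GMT and fold increase, secondary. Exposed only through missing placebo samples.

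**Placebo samples at stake.** Section 7.4.6 gives 966 evaluable adults in the immunogenicity and lot-to-lot groups (812 young, 154 elderly), randomized 6:1.

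- Young: 812/7 = 116. Elderly: 154/7 = 22. Total: 966/7 = 138. This reproduces the plan's 116 and 22.
- Adolescents with immunogenicity data: 154/7 = 22, for exploratory endpoints.
- For scale, core-group placebo subjects: 3850/7 = 550, or 495 after the plan's 10% drop-out.

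**Interval before Visit 5.** The last scheduled safety call is Day 85 (8.1.7). 197 − 85 = 112 days, and 112/196 = 57% of the time from Day 1 to Day 197. This is a share of calendar time, not of events.

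**What sample loss would cost (illustration).** Assume a log10 SD of 0.6 in both arms. That is the lot-consistency planning value in 10.2.2; the documents give no Day 197 SD. Take 828 vaccine subjects (696 + 132) and ignore the baseline covariate. The 95% half-width on the log10 scale is 1.96 × 0.6 × √(1/828 + 1/n), where n is the number of placebo samples.

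| Placebo samples lost | n | Half-width | CI factor for the GMT ratio (×/÷) |
|---|---|---|---|
| 0% | 138 | 0.108 | 1.28 |
| 10% | 124.2 | 0.113 | 1.30 |
| 25% | 103.5 | 0.123 | 1.33 |
| 50% | 69 | 0.147 | 1.40 |

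Moderate loss costs little precision. Only near-total loss would remove the comparison.

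**The case against.** **The protocol's stated rule is already the blinded order.** The synopsis, 7.1 and 7.3 all put unblinding after Visit 5. It is therefore wrong to say that the plan requires unblinded recording. That stands: the defect is a contradiction. It still matters, because 8.1.8 is the list a site works from and neither 8.1.8 nor 7.4.7 tells the site to finish the assessments first.

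**The lists may not be chronological.** Event recording also comes after vaccination at Visits 3 and 6 (8.1.4, 8.1.9), apparently as a template habit. That is fair, but at Visit 3 the earlier step does not reveal the arm to blinded staff, and by Visit 6 the arm is already known. Visits 2, 3 and 6 also list the blood draw ahead of the dose. At Visit 5 it is listed after the step that ends placebo participation.

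**Other routes capture events earlier.** SAE forms go to the CRO within 24 hours (9.5.6.8), weekly prompts after Day 57 cover COVID-19 and SAEs (7.1), and AEs found at unscheduled visits are classed as MAAEs (8.3). This stands. A reader might infer from the 112-day gap that 57% of the controlled safety data are gathered unblinded; the documents do not support that.

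**Placebo samples are protected elsewhere.** Section 7.1 brings all subjects back on Day 197, 7.4.8.2 encourages withdrawing subjects to complete the Visit 5 evaluations within 7 days, and 8.2 asks for the Visit 5 procedures in the lot-to-lot and immunogenicity groups. These reduce the risk, though the first is encouragement and the second says follow-up may be arranged. None of them restores blinding once the envelope is open.

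**Conclusion.** The concern holds as an internal contradiction about when the blind is broken. Sections 8.1.8 and 7.4.7 conflict with the synopsis, 7.1 and 7.3.

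If the 8.1.8 order is followed, two things result. MAAEs, SAEs, AESIs and ADEs first recorded at Visit 5 are reported and attributed with the arm known. Some placebo Day 197 samples are put at risk: at worst 138 evaluable adults, with only secondary GMT and fold-increase endpoints affected. The documents do not allow the number of events first recorded at Visit 5 to be estimated.

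Two broader readings should be resisted. One is that the primary safety data as a whole are collected unblinded: reactogenicity and unsolicited AEs to Day 57 are collected blind, and data after Day 197 are open by design. The other is that the 138 samples will be lost: no passage directs that, and several work against it.

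The conclusion assumes that at least some sites take the 8.1.8 numbering as the working order. If every site completes the assessments first, no data are harmed and only the text needs correcting.

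**What to change.** 1. Reorder 8.1.8: examination, vital signs and renal check; blood draw; concomitant medication; AE, SAE, MAAE, AESI and COVID-19 symptom recording with causality completed. Only then open the envelope, with placebo withdrawal as the last step.
2. Amend 7.4.7 so that the envelope is opened after all Visit 5 assessments are completed, and bring the looser statements in the synopsis and 7.1 into line.
3. For subjects already seen, flag events first recorded at Visit 5 after the code was opened. An analysis without those events is optional and only supplementary, because it would also drop genuine events from both arms.

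The cost is one reordered list, small wording changes and a site memo, plus a data flag if Visit 5 has begun. No visit, sample or test is added.
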